4.1 Screening/Baseline Visit procedures

At clinic sites, recruitment procedures will be implemented either by a clinical coordinator who is a regular member of the clinic staff or a research staff member working under the supervision of a clinic staff member. For participants recruited via the AR-POWER network or Creaky Joints, a research staff member will implement recruitment procedures.

Potential participants will be interviewed to assess eligibility. Eligible participants will complete a telephone interview and a baseline questionnaire delivered via the Internet using Qualtrics and REDCap. The telephone interview will ask the participant knowledge questions about RA and will assess their health literacy via the standardized Newest Vital Signs instrument. The baseline questionnaire will include a list of DMARDS currently available in the US for the treatment of RA. Participants will be asked to indicate the ones that they are currently using.

4.2 Intervention/Treatment procedures (by visits)

After participants complete the baseline questionnaire, they will be randomly assigned to one of four study groups: Other CMI without Gist Reasoning Training, Other CMI with Gist Reasoning Training, DrugFactsBox[®] without Gist Reasoning Training, and DrugFactsBox[®] with Gist Reasoning Training. Note that in most cases the “Other CMI” provided will be FDA approved Medication Guides. However, not all DMARDS are required to have a Medication Guide. In these cases, the investigators will provide CMI developed by the American Society of Health-System Pharmacists[®]. These materials are similar to the CMI that is given to patients in the United States when prescriptions are dispensed.

Participants will then be directed to a website that provides written prescription drug information (either Other CMI or DrugFactsBoxes[®], depending on group assignment) for the medications they are currently using. The website will allow participants to print a hard copy of the materials, if desired. The website will also allow them to access information about other DMARDS. For participants randomized to the gist training group (SMART Program), staff at the Center for BrainHealth at the University of Texas-Dallas will contact participants, either by email or by phone, to enroll them in the next SMART Program. The training program will be delivered in small groups of 5-6 individuals over a 1-month period. Each program will include 4 60-minute sessions delivered by research personnel certified to provide the program. Training will be presented via an online video conferencing platform, such as BlueJeans[®], that permits synchronous, audio and visual communication between trainers and participants. Participants only need a computer (desk, laptop, tablet) or mobile phone with internet access to participate.

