6.3 Statistical Methods

Preliminary Analyses: Characteristics of study participants will be presented, stratified by study group, using means and percentages, depending on the measurement properties of the variables involved. Statistical comparisons will be made using linear regression models for continuous variables and chi-square tests for categorical variables. All data analyses will be performed using SAS PC, version 9.4 (SAS Institute, Cary, NC).

Primary Analyses: The primary outcome variable is Informed Decision-Making assessed at the 6-month follow-up. The investigators will test the following hypotheses using logistic regression methods.

1. Participants will be more likely to meet the criteria for Informed Decision-Making at the 6-month follow-up if they were assigned to receive written medication information via the DrugFactsBox[®] format compared to the Other CMI format.
2. Participants will be more likely to meet the criteria for Informed Decision-Making at the 6-month follow-up if they were assigned to receive gist reasoning training, delivered via the SMART Program, compared to those who were not assigned to receive this training.
3. Participants will be more likely to meet the criteria for Informed Decision-Making at the 6-month follow-up if they were assigned to receive medication information via the DrugFactsBox[®] format **combined with** gist reasoning training, delivered via the SMART Program, compared to individuals in the other three groups.

The regression model will control for Informed Decision-Making at baseline (0=Did not meet criteria for Informed Decision-Making, 1=Met criteria for Informed Decision-Making) and indicator variables for each intervention indexing whether the participant was assigned to SMART Training (0=No, 1=Yes) and the DrugFactsBox[®] group (0=No, 1=Yes). In separate regression models, the investigators will also test three 2-way interactions. The first interaction will assess whether the effects of the two interventions are dependent of one another (Hypothesis 3). The other interaction terms will assess whether the effects of each intervention varies as a function of whether participants met the criteria for Informed Decision-Making at baseline. Statistical significance will be evaluated with alpha (2-tailed) set at 0.05. When significant interaction terms are observed, the investigators will use stratified analyses to examine the nature of the interaction.

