In the main analysis, the investigators will use an *intention-to-treat* strategy, with individuals included in the analysis based on random group assignment, without regard to whether they were actually exposed to the intervention. However, the investigators will only include participants with nonmissing data at the 6-month follow-up. In addition to the main analyses, the investigators will perform three sets of sensitivity analyses to

assess the robustness of the findings. The first set of sensitivity analyses will use an *as-treated* approach and include only people with nonmissing data at the 6-month follow-up. Individuals will be included in this analysis only if they actively participated in the interventions. For the DrugFactsBox[®]/Other CMI groups, the investigators defined active participation as viewing at least one page on the DrugFactsBox[®]/Other CMI website. For the SMART group, the investigators will define active participation as attending at least 3 of the 4 training sessions. Note that all individuals in the No SMART group will be included in the *as-treated* analyses because they will not have an opportunity to participate in any training. In the second set of sensitivity analyses, the investigators will use an *intention-to-treat* approach and impute missing data using the last-observation-carried forward method for individuals who do not complete the 6-month follow-up. In the final set of sensitivity analyses, the investigators will use as *as-treated* approach and impute missing data using the last-observation-carried forward method.

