Secondary Analyses: The investigators will use the same analytic strategy to examine the effect of the intervention on 18 secondary outcomes assessed at the 6-month follow-up: Medication Self-Management Knowledge, Selective Learning, Complex Abstraction, Lesson Quality, Use of the RA Self-Management Website, Participation in the BetterChoices,BetterHealth program, Self-Efficacy, Overall Medication Satisfaction, Global Treatment Satisfaction, Medication Adherence, Objective Health Literacy, Subjective Health Literacy, Disease Activity, Illness Intrusion, Illness Distress, Global Health, Depression, and Fatigue. In these analyses, the investigators will use either logistic or linear regression, depending on the measurement properties of the outcome variable. Due to the number of endpoints examined in these secondary analyses, the investigators will use the Hochberg method to adjust for the potential inflation of Type I error.⁸⁵

Exploratory Analyses: The investigators will use the same analytic strategy to evaluate intervention effects at the 6-week and 3-month follow-ups. However, these analyses will be considered exploratory and are designed to capture any transient intervention effects that may occur.

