Participants randomized to the SMART Program will be contacted by staff at the Center for BrainHealth at the University of Texas at Dallas following completion of baseline data collection, by email and telephone, to enroll them in the next SMART Program. The

program will be delivered by Center research personnel certified to provide the program using an online video conferencing platform that permits synchronous, audio and visual communication between trainers and participants. Participants will only need a computer or mobile phone with internet access to participate. Initially, the program will be delivered via four 60 to 90 minute sessions, spanning a one month period. In most cases, the program will be delivered in small groups with three to four participants. However, the program will be delivered one-on-one, if needed to accommodate participant schedules.

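### SMART is taught in live small groups, but the section 6.3 model treats all participants as independent; if outcomes correlate within groups, the H2 test runs modestly above 5%

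*Combined protocol and SAP*

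**What the plan says.** Delivery is described twice, differently. Section 4.2: "The training program will be delivered in small groups of 5-6 individuals over a 1-month period". Section 8: "In most cases, the program will be delivered in small groups with three to four participants", and "the program will be delivered one-on-one, if needed to accommodate participant schedules". Both sections describe a live video platform linking trainers and participants. Section 8 has the training centre contact SMART participants "to enroll them in the next SMART Program", so groups appear to form in order of enrolment. Participants not assigned to SMART receive no training.

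The primary model in section 6.3 is a logistic regression on baseline Informed Decision-Making and "indicator variables for each intervention indexing whether the participant was assigned to SMART Training (0=No, 1=Yes"), with the matching DrugFactsBox indicator. Interactions are tested in separate models. The main analysis is by assignment, "without regard to whether they were actually exposed to the intervention", among those with 6-month data. The as-treated analyses keep SMART participants only if active, defined as "attending at least 3 of the 4 training sessions". The same strategy is applied to 18 secondary outcomes, where "the investigators will use the Hochberg method to adjust for the potential inflation of Type I error".

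Section 6.4 sizes the trial at 300 (75 per arm) for 80% power to detect 60% v 35%, with two-sided alpha 0.05 and 15% attrition. Sections 6.3 and 6.4 contain no training-group term, random effect, robust variance, ICC or design effect.

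**The concern.** People trained together share sessions, discussion, a trainer and a calendar period. If that makes their outcomes more alike, the SMART half of the trial carries less information than its head count suggests, while the other half does not. A model that assumes independence then understates the standard error of the SMART effect. The H2 confidence interval is too narrow and the test rejects a true null more often than 5% of the time.

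SMART effects on the secondary outcomes inherit the problem. Some of these, such as gist reasoning and selective learning, are close to what the groups are taught. The Hochberg procedure presumes valid p-values, and a given understatement of the standard error inflates a small threshold proportionately more than it inflates 5%.

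**Working it through.** **1. The plan's own figure.** For 60% v 35%, two-sided 0.05 and 80% power, the usual two-proportion formula needs 62 per arm. Allowing for 15% loss, 62/0.85 rounds up to 73 per arm, or 292 in all, against 300 planned. With 75 × 0.85 = 63.75 analysed per arm, power is 81.5%. The stated 80% therefore reproduces as a comparison of two single arms. H2 compares halves, 150 × 0.85 = 127.5 a side, and has 98.2% power (98.5% with unpooled variance).

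**2. Inputs for clustering.** Group size m comes from sections 4.2 and 8, and 15% loss from section 6.4. Two inputs are assumed because the documents do not give them: an ICC of 0.01, 0.05 or 0.10, and, where used, a share q = 0.30 of SMART assignees trained one-on-one or never attending.

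**3. Formulas.** Loss thins each group, so the design effect in the SMART half is DE = 1 + 0.85(m − 1)ICC. Only one side is grouped, so the variance of the contrast rises by V = (1 + DE)/2. The actual two-sided error is 2[1 − Φ(1.96/√V)].

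**4. H2 with every SMART participant in a group.** At m = 4 and ICC 0.10: DE = 1 + 0.85 × 3 × 0.10 = 1.255, V = 1.1275, √V = 1.062, error 6.5%.

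| m | ICC 0.01 | ICC 0.05 | ICC 0.10 |
|---|---|---|---|
| 3.5 | 5.1% | 5.6% | 6.2% |
| 4 | 5.1% | 5.7% | 6.5% |
| 5.5 | 5.2% | 6.1% | 7.3% |
| 6 | 5.2% | 6.2% | 7.5% |

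Simulating the section 6.3 model under the null (35% event rate, assumed 25% baseline rate, 15% random loss, groups mixing both information formats, 20,000 runs per setting, Monte Carlo SE about 0.15 points) gave these rates at ICC 0/0.01/0.05/0.10: 4.7/5.1/5.9/6.5% for groups of 3-4, and 5.2/5.4/6.3/7.7% for groups of 5-6. If loss did not thin the groups, the formula at ICC 0.10 would give 6.8% (m = 4) and 8.0% (m = 6).

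**5. H2 with 30% outside groups.** The excess DE − 1 is multiplied by 0.7 if groups are refilled to size, or by 0.7² = 0.49 if absentees leave gaps. At ICC 0.10, m = 3.5 gives 5.9% refilled and 5.6% with gaps; m = 5.5 gives 6.6% and 6.1%. Simulation gave 5.6% and 5.4% for groups of 3-4, and 6.7% and 6.2% for groups of 5-6. At ICC 0.01 all these cases are 5.1-5.2%.

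**6. As-treated analyses.** Take the 30% as all non-attendance, so 127.5 × 0.7 = 89.25 SMART participants remain against 127.5. The variance ratio becomes V = (DE/89.25 + 1/127.5)/(1/89.25 + 1/127.5). With gaps, DE = 1 + 0.7 × 0.85(m − 1)ICC. At ICC 0.10 the error is 6.0% (m = 3.5) and 6.9% (m = 5.5). With groups refilled it is 6.5% and 7.7%.

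**7. Secondary outcomes.** If the Hochberg family is the 18 outcomes, the strictest step is 0.05/18 = 0.28%, with z = 2.991. At ICC 0.10 with everyone in groups, m = 3 gives 0.41% (1.5 times nominal) and m = 6 gives 0.66% (2.4 times).

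**8. Power and the remedy.** Using the clustered variance, power for 35% v 60% is 97.3% at DE 1.255 and 96.2% at DE 1.425, from 98.5% without clustering. In the simulations cluster-robust standard errors gave H2 error of 4.7-5.4% in every setting. Model-based H1 error was 4.6-5.2%, and H3 tested as an interaction 4.8-5.4%.

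**The case against.** The strongest reply is that under the delivery described in section 8 the effect is close to nil. Groups are mostly three to four, some people are trained alone, and intention to treat keeps non-attenders. At ICC 0.01-0.05 with 30% outside groups of that size, the error is 5.1-5.4%, within the range the remedy itself produced. The primary outcome is also an individual composite of knowledge, values and DMARD use, measured six months after baseline in people from scattered sites, so a large ICC is not obviously to be expected. The upper figures need ICC 0.10, groups of 5-6 and nobody trained alone, which section 8 contradicts. All of this stands, and it is why the point is minor. It does not remove the point: the model is misspecified for any positive ICC, and section 4.2 still says 5-6.

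Several stronger readings are tempting and unsupported:

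- **Non-attendance gives no dilution in the as-treated analyses.** It does if absentees leave gaps (step 6); dilution is reduced but not removed.
- **One-on-one delivery guarantees exactly 5%.** That holds only without shared-trainer correlation, which these figures do not cover. The documents do not say how many trainers there are.
- **Group membership goes unrecorded.** The documents do not say so. The attendance rule implies session-level records, so the identifier may already exist.
- **The 0.05/18 step is fixed.** Section 6.3 names 18 outcomes but does not define the Hochberg family, and each outcome has more than one contrast.

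**Conclusion.** The point holds as a conditional and modest one. If outcomes correlate within training groups, the section 6.3 model understates the SMART standard error. For an assumed ICC of 0.01 to 0.10, H2 runs at about 5.1-6.5% (groups of 3-4) or 5.2-7.7% (groups of 5-6) with everyone in groups, and at about 5.1-5.9% or 5.1-6.7% with an assumed 30% outside them. SMART effects on secondary outcomes are affected in the same way, with larger relative inflation at stricter thresholds.

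A reader might infer that the SMART estimate is biased, that the trial is too small, or that H1 and H3 are compromised. The documents support none of these. The intention-to-treat point estimate is unaffected and H2 power for a 25-point difference stays at about 96% or more. H1 and the H3 interaction are little affected provided groups mix both information formats, which is inferred from how participants are enrolled and is not stated. In practice only a borderline SMART p-value would change. The mismatch in group size between sections 4.2 and 8 needs correcting whatever the ICC.

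**What to change.** In section 6.3, specify cluster-robust standard errors, clustered on training group, for the SMART effect in H2, the secondary analyses and the as-treated analyses. Treat each non-SMART, one-on-one or never-enrolled participant as a cluster of one. Keep the training-group identifier in the analysis data set. Make section 4.2 and section 8 agree on group size, with the one-on-one exception stated in both. Report the ICC and the number and size of groups, and say whether groups mixed the two information formats.

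The cost is one field in the data set, a sentence in section 6.3 and a wording correction. No patients, visits or procedures are added. The price in precision is a SMART confidence interval wider by the factor √V: up to about 6% (m = 4, √1.1275 = 1.062) or 10% (m = 6, √1.2125 = 1.101) at ICC 0.10, and essentially unchanged at ICC 0. This is a cheap improvement of minor importance.

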4.3 Follow- up procedures (by visits)

Follow-up data will be collected 6-weeks, 3-months and 6-months after baseline. After the 6-week follow-up interview, all participants will be sent a letter that gives them the opportunity to participate in the online Better Choices, Better Health[®] program free of charge. This program is adapted from the Arthritis Self-Management Course developed by Lorig and colleagues. In the proposed study, the investigators will use participant acceptance of the offer to participate in the Better Choices, Better Health[®] program as a behavioral measure of patient interest in obtaining additional information about RA self-management and alternative treatment options.

4.4 Unscheduled visits

Not applicable

4.5 Concomitant Medication documentation

Not applicable

4.6 Rescue medication administration (if applicable)

Not applicable

4.7 Subject Completion/ Withdrawal procedures

The interventions tested involve minimal risk. Therefore, the investigators do not plan to withdraw individual participants for any reason. However, if a participant becomes upset concerning any study procedures, the investigators will ensure that they understand that they have the right to withdraw from the study at any time, without penalty. When participants express a desire to withdraw from the study, the investigators will solicit their reasons for withdrawing and document the reasons given.

4.8 Screen failure procedures

Individuals who were screened for study eligibility, but who did not meet the eligibility criteria, will be thanked for their interest in the study.

5 STUDY EVALUATIONS AND MEASUREMENTS (how measurements will be made)

5.1 Efficacy Evaluation (if applicable)

Efficacy data will be collected via a combination of telephone interviews and self-administered questionnaires, completed via REDCap. Measures included in the interviews and questionnaires are described below and summarized in Table 1.

Primary Outcome: The primary outcome variable for this study is Informed Decision-Making. Informed Decision-Making is typically conceptualized as making a decision, based on adequate knowledge, that is consistent with one's values.⁵⁰⁻⁵³ To operationalize this definition, the investigators will assess three variables: knowledge of RA and RA treatment options, values pertaining to the management of RA, and current DMARD use.

Knowledge will be assessed by three separate instruments administered via telephone interview: an 8-item measure developed by Fayet and colleagues⁵⁴ that assesses knowledge concerning methotrexate, which is often first-line therapy for RA; a 20-item measure developed by Fraenkel and colleagues⁵⁵ to assess knowledge concerning biologic treatment options; and an 8-item measure developed by Barton and colleagues⁵⁶ that assesses knowledge of RA and RA treatment options more generally.

Values. Questions included in the self-administered questionnaires will ask participants to indicate the extent to which they agree or disagree with 10 simple values statements (e.g., It is OK to ignore the risk of a serious side effect if it is extremely rare; It is better to

continue with the pain I know than to change my medications) developed by Fraenkel and colleagues.^{57,58} Responses will be recorded on a 4-point scale ranging from 1=*Strongly Agree* to 4=*Strongly Disagree*. Responses will be summed and rescored to yield a composite scale that ranges from -15 to +15, where positive numbers reflect values favoring the use of medications to control RA disease activity.

DMARD Usage will be assessed via the online questionnaires. Participants will be shown a checklist of 19 medications used to treat RA (abatacept, adalimumab, azathioprine, certolizumab pegol, cyclosporine, etanercept, golimumab, gold, hydroxychloroquine, infliximab, leflunomide, methotrexate pill, methotrexate shot, minocycline, rituximab, sulfasalazine, tocilizumab infusion, tocilizumab shot, and tofacitinib) and asked to check all of those that they are currently using. Participants will also be to check an option labeled *None of the above*. DMARD Usage will be scored as “0” if the participant reports using no DMARDS and “1” if the participant reports using one or more DMARDS.

Informed Decision-Making. Participants will be classified as meeting the criteria for informed decision making if they:

- (1) Answer at least 85% of the knowledge items correctly, score greater than 0 on the values scale indicating favorable attitudes concerning the use of medications to control disease activity, and are using a DMARD **OR**
- (2) Answer at least 85% of the knowledge items correctly, score 0 or less on the values scale indicating reluctance to use medications to control disease activity, and are not currently using a DMARD.

Individuals who fail to meet either set of criteria will be classified as not meeting the criteria for informed decision-making.

Proximal Secondary Outcomes: The investigators will assess five proximal secondary outcomes: Gist Reasoning Ability; Selective Learning; Information Seeking; and two specific types of knowledge, Verbatim Recall and Medication Self-Management Knowledge. These variables, which are described below, are considered proximal because the investigators conceptualize them as direct effects of the intervention.

Gist Reasoning Ability, also referred to as integrated reasoning, will be assessed by the Test of Strategic Learning (TOSL). The TOSL was developed by Chapman and colleagues to systematically quantify participants’ capacity to synthesize and interpret high-level meaning from lengthy multi-faceted textual information.^{59,60} The TOSL consists of four text passages of similar length and complexity. At each data collection point, participants will read one of the text passages presented via an online learning platform. (The texts, as well as their order of presentation, will be randomized at each assessment so that participants will not see the same text twice.) Participants will not be allowed to return to the passage once they finished reading. After reading the passage,

participants will be asked to provide a synthesized, condensed version of the text in their own words, conveying primarily high-level ideas of substance rather than specific details. They will be given five minutes to complete this task. Participants will then be asked to generate as many interpretations (i.e., lessons learned) as possible that could be derived from the passage. They will be given three minutes to complete this task.

Responses will be scored using a manualized, objective scoring system by a trained and experienced rater, based at the Center for BrainHealth, who is blinded to participants' group assignment and time point of testing. Two separate scores will be derived from participant responses: number of abstracted ideas (Complex Abstraction) and a weighted index reflecting the quantity and quality of high-level interpretations (Lesson Quality). High-level interpretations will be judged against a rubric based on the specific content of each passage.

Selective Learning is defined as the ability to optimize processing of incoming information by controlling working memory to try to remember high value information while inhibiting low value information.⁶¹ To assess this ability, the Visual Selective Learning (VSL) task will be administered as part of each telephone interview by showing participants 3 lists of 16 words via a PowerPoint presentation imbedded in a YouTube video. Each word will appear on a separate screen for 1 second. Half of the words will be in uppercase and half will be in lowercase. In some trials, participants will be instructed that uppercase words are valued at 10 points and lowercase words at 1 point; in other trials, the point value was the opposite. Participants will be told to remember as many words as they could, but that their goal is to earn as many points as possible. Different word lists will be used at each time point and the lists will be balanced across participants over the course of the study using procedures parallel to those for the TOSL. At each time point, scores will be summed across the three lists, yielding a composite score with a possible range from 0 to 264.

Information Seeking will be assessed using two behavioral measures incorporated into the design of the study. First, the investigators will create a website that provides easy access to information about RA, treatment options, and self-management strategies. The investigators will refer to this website at the RA Self-Management Website. Participants will be emailed a link to this website immediately after completion of 6-week follow-up data collection. The investigators will use Google analytics to track whether participants accessed the website and the specific website pages viewed. Second, immediately after completion of 6-week follow-up data collection, the investigators will email all participants an invitation to take part in BetterChoices, BetterHealth®, an online chronic illness self-management program, free of charge. The investigators will track whether or not participants enroll in the class, the number of class sessions attended, and whether or not participants complete the class.

Verbatim Recall of information concerning potential medication benefits and harms will be assessed by medication-specific items developed specifically for this study. For each medication, the investigators will identify one potential benefit and one potential harm listed in the Drug Facts Box. Each question will ask participants about the probability of benefit/harm using a multiple-choice response format. To minimize response burden, participants will be asked these questions in relation to only one of their current RA medications. For participants taking more than one RA medication, the investigators will ask the items in relation to methotrexate, if methotrexate is being used. Otherwise, the investigators will ask the items in relation to the most commonly used biologic medication the participant is using or, in cases where the participant is not using any biologic medications, the investigators will ask the items in relation to a non-biologic medication. Correct responses will be summed across the benefit and harm items to yield a score ranging from 0 to 2. This measure will be administered, by telephone interview, only at the 6-week follow-up.

Medication Self-Management Knowledge will be assessed using a 45-item medication-specific measure tailored to the medications each participant reports using and developed specifically for this study. For participants using methotrexate, the items will focus on this medication. For participants not using methotrexate but using a biologic, the items will focus on the most commonly used biologic. Otherwise, the items will focus on a non-biologic. The first 42 items will involve a list of possible medication side-effects, some that are known risks for the targeted medication and some that are not. For each side-effect, participants will be asked whether or not they would call the doctor immediately if they experienced the side-effect. (Consumer medication information (CMI) typically includes information concerning those side-effects that require immediate medical attention.) The final three questions will be scenario-based and designed to assess knowledge of other aspects of medication use (e.g., whether medication should be stored in the refrigerator, what to do if medication is accidentally frozen, whether it is OK to get a flu shot when taking the medication). These questions will draw on information found in the medication information provided to participants. Correct answers will be summed across the 45 items and then transformed to a 100 point scale, reflecting the percentage of questions answered correctly.

Intermediate Secondary Outcomes: The investigators will assess three intermediate secondary outcomes: Treatment Satisfaction, Satisfaction with Medication Information, and Arthritis Self-Efficacy

Treatment Satisfaction will be assessed by the 9-item abbreviated Treatment Satisfaction Questionnaire for Medication (TSQM-9).⁶²⁻⁶⁴ Items ask participants to rate their satisfaction with different aspects of their treatment regimen on a 7-point scale with endpoints labeled as “extremely satisfied” and “extremely dissatisfied”. The TSQM-9 has three subscales: Effectiveness, Convenience, and Overall Satisfaction. Internal

consistency has been demonstrated in past research with Cronbach's alpha exceeding 0.80 for each subscale.⁶² The Overall Satisfaction subscale has demonstrated the greatest sensitivity to change following changes in therapy.⁶⁵

Satisfaction with Medication Information will be assessed using the 17-item Satisfaction with Information about Medicines Scale (SIMS).⁶⁶ Items ask participants to rate the amount of information they have received about different aspects of their medications (e.g., what the medicine is for, how it works, whether it has side-effects). Responses range from "too much information" to "no information needed". Responses are summed to yield a total score with higher scores reflecting greater satisfaction with amount of information received. In developmental studies, Cronbach's alpha for the total score ranged from 0.81 to 0.91 across eight different chronic illness subgroups.⁶⁶ The SIMS has also been shown to be sensitive to change following participation in a patient-centered counseling intervention.⁶⁷

Arthritis Self-Efficacy will be assessed using the 8-item Arthritis Self-Efficacy Scale.^{68,69} Items assess confidence in one's ability to manage arthritis pain in different situations (e.g., keep pain from interfering with things you want to do). Responses will be recorded on a 10-point scale with endpoints labeled "very uncertain" and "very certain". This measure has been widely used in arthritis patient populations and has been shown to have excellent psychometric properties, including high internal consistency (Cronbach's alpha generally exceeds 0.90) and sensitivity to change following participation in illness self-management programs.^{70,71}

Distal Secondary Outcomes: The investigators will assess six distal outcome variables reflecting different aspects of health-related quality of life: Illness Intrusiveness, Health Distress, Depression, Fatigue, Disease Activity, and Global Health Status. Our remaining distal outcome variables were Objective Health Literacy, Subjective Health Literacy, and Medication Adherence.

Illness Intrusiveness will be assessed using the 13-item Illness Intrusiveness Ratings Scale. Participants will be asked to rate the degree to which their "illness and/or its treatment" interferes with activities that are essential for quality of life (e.g., work, recreation, finances, social relationships).⁷² Responses will be recorded on a 7-point response scale with endpoints labeled, "not very much" and "very much." The instrument can be scored by either summing across all items to obtain a total score or computing separate scores for three subscales: relationships and personal development (family relationships, social relationships, community and civic involvement), intimacy (relationship with partner and sex life), and instrumental (work, finances). Cronbach's alpha for the total score, which The investigators used in this study, has been found to range from 0.78 to 0.97 across 36 different health conditions.⁷³

Health Distress will be assessed by the 4-item measure developed by Lorig and colleagues.⁷⁴ This measure was adapted from the Medical Outcomes Study health distress scale for use in arthritis populations.⁷⁵ The adapted measure has demonstrated high internal consistency and responsiveness to change following completion of an arthritis self-management course.⁷⁴

Depression and **Fatigue** will be assessed using the computer adaptive testing version of the Neuro-QOL (Quality of Life in Neurological Disorders) version 1.0 item bank.⁷⁶⁻⁷⁸ These measures will be administered using the Assessment CenterSM Application Programming Interface (API) which is available through REDCap. The measures will be automatically scored by the API. Neuro-QOL measures have undergone substantial testing in previous research and have demonstrated both reliability and validity across diverse patient populations.⁷⁸

Disease Activity will be assessed using the RAPID3 (Routine Assessment of Patient Index Data).^{79,80} This patient-reported outcome measure has three components: physical function, pain, and global illness impact (i.e., “Considering all the ways in which illness and health conditions may affect you, please indicate how you are doing?”). Scores for each component are equally weighted and summed to calculate a total score. This measure has been shown to distinguish between active and control treatments in two clinical trials evaluating the efficacy of a biologic RA medication. In addition, the RAPID3 is one of the disease activity measures identified in the 2012 American College of Rheumatology Guidelines for the treatment of RA, which recommend using a treat-to-target strategy based on current disease activity.¹⁰

Global Health Status will be assessed by a single item asking participants to rate their current health on a 5-point scale from “1=Excellent” to “5=Poor”. This item has been shown to predict mortality and health care utilization as well as multi-item health status measures.⁸¹

Health Literacy. The investigators will assess health literacy using both subjective and objective measures. The subjective measure, developed by Chew and colleagues^{82,83}, includes three items: “How confident are you filling out medical forms by yourself?”, “How often do you have someone (like a family member, friend, hospital/clinic worker or caregiver) help you read hospital materials?”, and “How often do you have problems learning about your medical condition because of difficulty reading written material?” Each item will be answered on a 5-point scale ranging from 0 to 4, with higher values reflecting lower health literacy. In past research these items have demonstrated construct validity by correctly classifying individuals determined to have inadequate health literacy using either the REALM or the S-TOFHLA.⁸³ In the current study, the investigators will sum participant responses across the three items and reverse score the sum to yield a summary score with higher values reflecting higher health literacy.

The investigators will assess objective health literacy using the Newest Vital Sign (NVS).⁸⁴ This measure asks participants to look at the nutrition label from a pint container of ice cream. While looking at the label, participants are asked six questions (e.g., “If you ate the entire container, how many calories would you eat?”). Correct answers will be summed and then transformed to a 100 point scale, reflecting the percentage of questions answered correctly. In previous research, this measure has demonstrated internal consistency (i.e., Cronbach alpha =0.76) and construct validity (strong correlations with TOFHLA). Because the investigators will administer this measure twice in the current study, the investigators were concerned that memory effects would artificially inflate scores at the second assessment. Therefore, the investigators created a second version of the NVS based on the same ice cream container label, but with slightly modified questions. Participants will complete one version at baseline, determined randomly and balanced across participants, and the other version at the 6-month follow-up.

Medication Adherence will be assessed by a single question that asks: “All things considered, how much of the time do you use your RA medications EXACTLY as directed?” Responses will be recorded on a 100-point visual analog scale with endpoints labeled “None of the Time” and “All of the time”.

Other Participant Characteristics: For descriptive purposes, The investigators will also collect the following socio-demographic information from study participants: age; gender (male, female); race (African-American, American Indian or Alaskan Native, Asian, Native Hawaiian, or Other Pacific Islander, White, Other); ethnicity (Hispanic, non-Hispanic); education (less than high school, high school diploma only, some college or technical school, college degree); marital status (never married, married, widowed, divorced, separated); and ability to afford medications (no trouble, a little trouble, a lot of trouble).

